6.7 End-of-Treatment and End-of-Trial Evaluations

6.7.1 Discontinuation of Subjects

Subjects will be free to discontinue trial participation at any time. The investigator will also discontinue any subject from the trial if, in the investigator's opinion, it is not safe for the subject to continue. The date the subject is withdrawn from a treatment and/or from the trial and the reason for discontinuation will be recorded on the CRF.

Trial participation will be considered completed if the subject has met all of the following trial requirements:

- Has received three contrast-enhanced ultrasound exams
- Has undergone the one month contrast-enhanced follow up MRI scheduled as part of their clinical care.

If a subject's participation in the trial is interrupted for any reason (e.g., because of an AE or if the subject is lost to follow-up) and the subject has met the criteria described above for completing the trial, the subject's trial participation will be considered completed. If a subject's trial participation is interrupted for any reason by the subject's or investigator's choice and the subject has not met all of the criteria listed above, then the subject will be considered a discontinued subject.

7. DATA MANAGEMENT AND STATISTICAL ANALYSES

7.1 Data Management

Data forms will be completed for all subjects enrolled in the trial. The subject study files will be stored in a secure file cabinet and maintained by the research study coordinator. Subject study files will be kept for 7 years after the completion of the study.

The final data will be entered into a database. The investigator will be responsible for management of the database. The database will be maintained within an organized and secure directory system.

7.1.1 Sub-Site Data Management

Data forms will be completed by sub-site research staff for all subjects enrolled at the sub-site. Completed data forms must be sent to Thomas Jefferson University for inputting into the database. Image data will be de-identified, transferred to Thomas Jefferson University, and placed on a secure server.

7.2 Statistical Analyses

Data analysis from this multi-center clinical trial will be performed to characterize 2D and 4D CEUS as a follow-up imaging tool for the evaluation of residual tumoral blood flow in patients with HCC treated with TACE.

Our statistical analysis will address three major questions:

1. Does 2D and 4D CEUS 1-2 weeks post TACE yield sensitivity and specificity greater than 90% for identifying residual tumor blood flow, thereby providing reliable earlier identification (relative to the current clinical standard) of patients in need of retreatment?
2. Does 2D and 4D CEUS 1 month post TACE yield sensitivity and specificity greater than 90% for identifying residual tumor blood flow, thereby providing an accurate, safe, and cost-effective imaging alternative for identifying TACE patients in need of retreatment?
3. Are quantifiable biomarkers generated by parametric imaging of 2D and 4D CEUS exams able to differentiate between fully treated and incompletely treated masses by measuring blood flow kinetics?

The first three cases at each institution will be used as reader training cases and will not be included in the final analysis. In the event of all cases showing identical response (i.e. all incompletely or completely treated), the first case with an alternative outcome will be substituted for the 9th case. Following reader training, each reader (all of whom have previous experience with CEUS and volumetric ultrasound) will be asked to evaluate all 201 remaining cases. 2D and 4D CEUS exams will be read separately and only after randomization. 2D cases will be viewed in a standard DICOM viewer, while 4D cases will be viewed in GE's 4D View software. Readers will first be asked to review both the patient's baseline CE-MRI/CT and CEUS exams to identify the size and location of the treated mass. Following baseline review, each reader will review the 1-2 week and 1 month CEUS exam (in random order). Intratumoral blood flow will be assessed as present or not present. Readers will then be asked to interpret the patient's 1 month follow-up CE-MRI/CT images and again evaluate the need to retreat based on residual blood flow. Finally, when available, readers will review subsequent CE-MRI/CT imaging studies (up to six months post TACE). MRI/CT evaluations will be based on mRECIST criteria. All imaging studies will be read twice by each

reader. Studies will be presented in random order. The second round reads will be performed at least one month after the first. Outcomes will be defined as incompletely treated (i.e. requiring retreatment) based on (in order of preference of reference standard): a) pathological examination of explanted livers demonstrating live tumors; b) tumor enhancement seen with CT or MR and confirmed via angiography during retreatment; c) tumor growth on 6 month follow-up CE-CT/MRI; or d) asymmetrical or nodular tumor enhancement on CE-MRI/CT on 6 month follow-up. Incomplete treatment on CEUS (2D or 4D) will be evaluated by each reader and evidenced by the tumor showing either residual blood flow after treatment or nodular peripheral blood flow.

For questions 1-2, sensitivity (the ability to detect patients in need of retreatment) and specificity (the ability to identify patients who do not require retreatment) will first be calculated on a reader by reader basis. Four 2 x 2 tables will be constructed comparing the need for re-treatment based on the clinical gold standard described above and CEUS, tabulating true positives, false positives, false negatives, and true negatives. A table will be created for CEUS at 1-2 weeks and 1 month for both 2D and 4D CEUS and used to calculate sensitivity, specificity, accuracy, positive predictive value, and negative predictive value. Statistical significance between the reference standard and each of the 4 CEUS groups will be determined using a McNemar test. These values will also be calculated based on the majority decision (i.e. 4 or more readers in agreement). In the event of discordant readings during this analysis, tumor outcome will be decided by consensus by the two readers at TJU. Differences between techniques (2D vs. 4D) and time points (1-2 weeks vs. 1 month post treatment) will be determined by comparing areas under the receiver operating characteristic curves for each modality/time point based on necessity of tumor retreatment. Intra-rater and inter-rater variability will be calculated using a Shrout and Fleiss Interclass Correlation [Shrout and Fleiss 1979]. Finally, a logistical regression and analysis of variance will be performed to determine if significant variations exist between individual sites (to determine operator dependence), lesion size (tumor size dependency) or between patients treated with cTACE vs. DEB-TACE (treatment dependency).

For statistical question 3, all quantitative parameters will be compared between fully treated and incompletely treated masses using a Student's t-test. Additionally, lesions that demonstrate lack of residual enhancement at 1 month, but show recurrence at 6 month follow-up, will be compared to completely treated masses to determine if quantitative CEUS parameters can detect this lower level of residual disease. Statistical analysis will be performed with assistance from the biostatistician co-investigator using Stata 12.0 (Stata Corp, College Station, TX) with p values < 0.05 considered statistically significant after a Bonferroni-type adjustment for multiple tests. These statistical tests will answer our three major questions regarding the sensitivity and specificity of 2D and 4D CEUS as an imaging tool for the follow-up of TACE

at 1-2 weeks and 1 month (specific aims 1-2), as well as the influence of operator, reader, tumor size, and embolization material.

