The first three cases at each institution will be used as reader training cases and will not be included in the final analysis. In the event of all cases showing identical response (i.e. all incompletely or completely treated), the first case with an alternative outcome will be substituted for the 9th case. Following reader training, each reader (all of whom have previous experience with CEUS and volumetric ultrasound) will be asked to evaluate all 201 remaining cases. 2D and 4D CEUS exams will be read separately and only after randomization. Readers will first be asked to review both the patient's baseline CE-MRI/CT and CEUS exams to identify the size and location of the treated mass. Following baseline review, each reader will review the 1-2 week and 1 month CEUS exam (in random order). Intratumoral blood flow will be assessed as present or not present. Readers will then be asked to interpret the patient's 1 month follow-up CE-MRI/CT images and again evaluate the need to retreat based on residual blood flow. Finally, when available, readers will review subsequent CE-MRI/CT imaging studies (up to six months post TACE). MRI/CT evaluations will be based on mRECIST criteria. All imaging studies will be read twice by each reader. Studies will be presented in random order. The second round reads will be performed at least one month after the first. Outcomes will be defined as incompletely treated (i.e. requiring retreatment) based on (in order of preference of reference standard): a) pathological examination of explanted livers demonstrating live tumors; b) tumor enhancement seen with CT or MR and confirmed via angiography during retreatment; c) tumor growth on 6 month follow-up CE-CT/MRI; or d) asymmetrical or nodular tumor enhancement on CE-MRI/CT on 6 month follow-up. Incomplete treatment on CEUS (2D or 4D) will be evaluated by each reader and evidenced by the tumor showing either residual blood flow after treatment or nodular peripheral blood flow.

For statistical questions 1-2, sensitivity (the ability to detect patients in need of retreatment) and specificity (the ability to identify patients who do not require retreatment) will first be calculated on a reader by reader basis. Four 2 x 2 tables will be constructed comparing the need for re-treatment based on the clinical gold standard and CEUS, tabulating true positives, false positives, false negatives, and true negatives for CEUS

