6.5 Efficacy Assessments

Following reader training, each reader (all of whom have previous experience with CEUS and volumetric ultrasound) will be asked to evaluate all 201 remaining cases. 2D and 4D CEUS exams will be read separately and only after randomization. Readers will first be asked to review both the patient's baseline CE-MRI/CT and CEUS exams to identify the size and location of the treated mass. Following baseline review, each reader will review the 1-2 week and 1 month CEUS exam (in random order). Intratumoral blood flow will be assessed as present or not present. Readers will then be asked to interpret the patient's 1 month follow-up CE-MRI/CT images and again evaluate the need to retreat based on residual blood flow. Finally, when available, readers will review subsequent CE-MRI/CT imaging studies (up to six months post TACE). MRI/CT evaluations will be based on mRECIST criteria. All imaging studies will be read twice by each reader. Studies will be presented in random order. The second round reads will be

performed at least one month after the first. Outcomes will be defined as incompletely treated (i.e. requiring retreatment) based on (in order of preference of reference standard): a) pathological examination of explanted livers demonstrating live tumors; b) tumor enhancement seen with CT or MR and confirmed via angiography during retreatment; c) tumor growth on 6 month follow-up CE-CT/MRI; or d) asymmetrical or nodular tumor enhancement on CE-MRI/CT on 6 month follow-up. Incomplete treatment on CEUS (2D or 4D) will be evaluated by each reader and evidenced by the tumor showing either residual blood flow after treatment or nodular peripheral blood flow.

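### The reading plan does not say that 1-2 week CEUS reads are locked before the 1 month exam, or CEUS reads before follow-up MRI/CT, so early reads may draw on later images

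*Combined protocol and SAP*

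**What the plan says.** The reading sequence appears three times in the same form: in the synopsis (Statistical Methodology), in section 6.5 and in section 7.2. After looking at baseline images, "each reader will review the 1-2 week and 1 month CEUS exam (in random order", and blood flow is called present or absent. Next, "Readers will then be asked to interpret the patient's 1 month follow-up CE-MRI/CT images". The last step is "Finally, when available, readers will review subsequent CE-MRI/CT imaging studies (up to six months post TACE". Further, "All imaging studies will be read twice by each reader", with at least a month between rounds, and "Studies will be presented in random order".

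The one separation that is stated concerns the imaging mode: "2D and 4D CEUS exams will be read separately and only after randomization". No section says that a read is locked before the next image is opened, or that readers are masked to other time points. Section 5.4 deals with blinding of the trial drug only. Section 7.1.1 has images de-identified before transfer.

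Question 1 in section 7.2 asks whether sensitivity and specificity at 1-2 weeks exceed 90%, "thereby providing reliable earlier identification (relative to the current clinical standard) of patients in need of retreatment". Section 7.2 also compares the two time points by ROC area and calculates intra-rater agreement. It does not say which reading round supplies the 2 x 2 tables.

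**The concern.** Question 1 is about what CEUS can tell a clinician at 1-2 weeks, when no 1 month exam exists. A 1-2 week read made, or revised, with the 1 month exam already seen does not measure that. Borrowing can also run the other way, from the early exam to the 1 month read. That is not future information, but it pulls the two sets of calls together and blurs the planned comparison of time points.

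A second route runs through the repeat reads. In the sequence as written, a reader has seen a patient's 1 month MRI/CT, and possibly imaging up to six months, before reading that patient's CEUS again. This affects intra-rater agreement. It affects accuracy only if second-round reads enter the 2 x 2 tables.

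Once readers have seen the later images, the same readers cannot make a clean early read, so the order has to be settled before reading starts.

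**Working it through.** **1. The plan's own figure.** Section 7.2.1 gives H0 90%, H1 98%, alpha 0.05 and, in the N = 200 row, 133 diseased and so 200 - 133 = 67 non-diseased. Take the exact one-sided binomial test, with cutoff the smallest c such that P(X >= c | n, 0.90) <= 0.05.

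- Specificity: n = 67, c = 65, actual alpha 0.0307, power at 98% 0.8494.
- Sensitivity: n = 133, c = 126, actual alpha 0.0385, power at 98% 0.9945.

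These match the table and the stated 85% and 99%. Nothing here disputes the sample size.

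**2. How many reads are exposed.** If each patient's two follow-up exams are opened together in 1:1 random order, half of the 1-2 week reads follow the 1 month exam and half of the 1 month reads follow the early one. The plan does not state the 1:1 ratio. If exams are shuffled across patients, effective exposure is much smaller.

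**3. A simple model of borrowing.** Let s be the share of reads opened after the other time point, f the fraction of those that adopt the other exam's call, and pe and pm the true accuracies at 1-2 weeks and 1 month.

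- Apparent early accuracy = pe + s x f x (pm - pe)
- Apparent 1 month accuracy = pm - s x f x (pm - pe)

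The documents give no value for s or f and no difference between pe and pm. **If pe = pm, both shifts are zero.** That is the sample size assumption, 98% with no distinction by time point.

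**4. Illustration with an assumed gap, pe = 90%, pm = 98%.** False success is the chance that the 1-2 week test passes when true accuracy equals the null.

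| s | f | Early / 1 month apparent | Difference (points) | False success, specificity / sensitivity | 1 month specificity power |
|---|---|---|---|---|---|
| none | none | 90.0 / 98.0% | 8.0 | 3.1 / 3.85% | 85% |
| 10% | 20% | 90.16 / 97.84% | 7.7 | 3.35 / 4.36% | 82% |
| 50% | 10% | 90.4 / 97.6% | 7.2 | 3.8 / 5.2% | 78% |
| 50% | 20% | 90.8 / 97.2% | 6.4 | 4.7 / 7.0% | 71% |
| 50% | 50% | 92.0 / 96.0% | 4.0 | 8.8 / 15.7% | 50% |

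Example for s = 50%, f = 20%: 0.90 + 0.5 x 0.2 x 0.08 = 0.908; P(X >= 65 | 67, 0.908) = 4.7%; P(X >= 126 | 133, 0.908) = 7.0%.

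**5. Both measures together.** Question 1 asks for sensitivity and specificity. These come from separate patients, so the chance that both pass when both are truly 90% is the product:

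- no borrowing: 0.0307 x 0.0385 = 0.12%
- s = 50%, f = 20%: 0.0474 x 0.0701 = 0.33%
- s = 50%, f = 50%: 0.0882 x 0.157 = 1.4%

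**6. Multiplicity.** If the Bonferroni-type adjustment is a split over four tables (0.05 / 4 = 0.0125), the cutoffs become 66/67 and 128/133. At s = 50%, f = 20%, false success moves from 0.73% to 1.21% (specificity) and from 0.66% to 1.40% (sensitivity).

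**7. Opposite direction.** With pe = 90% and pm = 85%, s = 50%, f = 20%, apparent early accuracy is 0.90 + 0.1 x (-0.05) = 89.5%, and false success falls to 2.3% / 2.6%.

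**8. Always reading 1-2 weeks first.** No early read is then exposed, but every 1 month read is. With the 90/98 gap and f = 20%, 1 month accuracy appears as 0.98 - 0.2 x 0.08 = 96.4%, the difference is 6.4 points and 1 month specificity power is 56%.

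The McNemar tests, ROC areas and majority reads are not modelled. Second-round exposure is not quantified, because the plan does not say whether those reads enter the tables.

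**The case against.** The strongest objection is that the plan may already shuffle exams. Elsewhere the protocol uses the word study for a single exam (the synopsis on the three CEUS visits; section 3.1) and calls patients cases. On that usage, "Studies will be presented in random order" would randomise exams across patients, and carry-over would be close to nil (the s = 10% row). This stands as a possible reading. The per-patient order of steps around that sentence points the other way, so the text does not settle it.

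The plan also has real safeguards: CEUS comes before MRI/CT in round one, rounds are at least a month apart, images are de-identified, and volume is high (up to 201 x 2 modes x 2 time points = 804 CEUS reads per reader per round). These weaken recall between rounds. They do not separate one patient's two exams if these are read one after the other.

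It is also fair that every adverse figure above needs an accuracy gap between time points that the documents do not state, and that single-test false success rates overstate the risk for a joint question. Both points stand.

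A reader might infer more than the text supports:

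- That the trial will overstate early accuracy. The direction is unknown and the shift may be zero.
- That first-round CEUS reads are made with MRI/CT in view. The stated order is the reverse. What is missing is a lock, and a statement of whether MRI/CT is opened between the 2D and the 4D reads.
- That second-round exposure biases sensitivity and specificity. That follows only if those reads enter the tables.

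**Conclusion.** The point holds as a gap in the reading plan that should be closed before reads begin. Run patient by patient, the sequence lets some 1-2 week reads (about half under 1:1 ordering) draw on an exam from the future, which weakens the answer to Question 1 and the time-point comparison. Second-round CEUS reads follow sight of follow-up MRI/CT, which weakens intra-rater agreement.

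The size cannot be derived from the documents. It is nil in this model under the plan's equal-accuracy assumption, and small if exams are shuffled. Under an assumed 90/98 gap with half of reads exposed, it is a shift of 0.4 to 2.0 points in apparent early accuracy for f of 10% to 50%. The conclusion rests on the read order and the absence of a lock, not on these illustrations.

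**What to change.** Amend sections 6.5 and 7.2 and the synopsis, keeping the same readers, images and number of reads:

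1. Present the 1-2 week and 1 month CEUS exams as separately coded items, shuffled across patients, each shown with baseline only and locked before the other is opened. At minimum, allow no 1-2 week read to be made or changed after the 1 month exam is opened. The minimum protects Question 1; only the full version also protects the time-point comparison.
2. Lock all first-round 2D and 4D CEUS reads before follow-up MRI/CT is released to that reader.
3. Name first-round reads as primary for the 2 x 2 tables and use second-round reads for intra-rater agreement. If the timeline allows, withhold MRI/CT until both CEUS rounds are complete; otherwise report intra-rater agreement with that caveat.

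The cost is a few sentences and a changed reading order. Baseline images are opened more often, and MRI/CT reads start later. The optional part of item 3 is the expensive one. MRI/CT is also read twice, so two gaps of at least a month would run in series, which alone equals the 2 months that section 3.1 allows for analysis and publication unless reading starts during recruitment.

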4.1 Inclusion Criteria

All subjects accepted for this trial must:

- Patients \geq 21 years of age
- Patient capable of making informed decisions regarding his/her treatment
- Scheduled for TACE treatment of a HCC mass (lesions reported as Liver Imaging Reporting and Data Systems 4B or 5 or Organ Procurement and Transplantation Network 5a or 5b)
- Negative pregnancy test in a female of child-bearing age (regardless of sexual orientation, having undergone a tubal ligation, or remaining celibate by choice) who meets the following criteria
 - Has not undergone a hysterectomy or bilateral oophorectomy; OR
 - Has not been naturally postmenopausal for at least 12 consecutive months (i.e., has had menses at any time in the preceding 12 consecutive months)
- Have an HCC mass viewable on grayscale B-mode ultrasound.

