6.2 Screening Assessments

Trial participants will have the presence of inclusion criteria and absence of exclusion criteria verified by providing a medical history. A full history and physical examination will be obtained from the patient's referring physician. If the subject is a woman of childbearing age as defined in the inclusion criteria (section 4.1), she will have a urine pregnancy test prior to each CEUS study (the results of which will be made available to the subject prior to study initiation). In the event a patient presents with a lesion that is expected to be difficult to view on ultrasound (for example, smaller lesions located high on the liver dome), grayscale ultrasound imaging will quickly be performed to ensure the lesion is visible on ultrasound and that the patient is suitable for study inclusion. Based on preliminary studies, approximately 10-30% of TACE patients will present with lesions that are not detectable on baseline ultrasound (generally a smaller, nonvisible percentage compared to traditional liver mass ultrasound characterization studies). Particular issues tend to arise in cirrhotic patients with smaller lesions at the dome of the liver [Kono et al. 2007]. Patients with masses not visible on B-mode ultrasound will be treated as failed cases and reported, but not followed with CEUS or counted towards our 210 enrollment limit for the work proposed in our specific aims.

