frequency pairings in the contrast imaging software will be used (transmitting at 2 MHz, receiving at the 4 MHz harmonic), and gain settings will be adjusted to minimize nonlinear signals prior to contrast injection. Additionally, the focal zone will be placed at the approximate depth of the lesion to maximize the generation of nonlinear signals during CEUS. During the first contrast injection, 2D CEUS will be performed using the coded harmonics nonlinear imaging package on the unit. The approximate tumor mid-line will be imaged until homogenous liver enhancement is achieved (approximately 45 seconds post injection), followed by imaging sweeps through the tumor. Sweeps will then be acquired in the sagittal plane, before returning to the original plane. Imaging will be continued until contrast washout is observed (approximately 3-4 minutes), after which data will be digitally stored for later review. A ten to fifteen minute wait period will be observed between injections to allow for complete ultrasound contrast agent clearance. A region of interest encompassing the entire tumor volume and margin will then be selected in 4D mode. Baseline imaging of the tumor will be repeated in 4D mode in grayscale B-mode. The line density (a measure of image quality) may also be adjusted to achieve adequate volume acquisition rates (>0.5 volumes/ second). A second bolus injection of up to 0.6 ml Definity followed by 10 cc saline flush will again be administered during continuous tumor imaging in 4D, which uses the machine's coded harmonics package. If sufficient contrast is not detected in either mode, the injection may be repeated with the total cumulative study dose not to exceed 1.5 ml. Data will be obtained until contrast washout is observed and then digitally stored in digital imaging and communications in medicine (DICOM) format for later review.

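### Follow-up 2D and 4D CEUS exams can be read only as flow or no flow, so a non-diagnostic exam has no place on the form and no analysis rule

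*Combined protocol and SAP*

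**What the plan says.** The only imaging requirement for entry is in section 4.1: "Have an HCC mass viewable on grayscale B-mode ultrasound". Section 6.2 gives the one rule for a visibility failure, and it applies at baseline: "Patients with masses not visible on B-mode ultrasound will be treated as failed cases and reported, but not followed with CEUS". The same section expects that "approximately 10-30% of TACE patients will present with lesions that are not detectable on baseline ultrasound".

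The 4D exam asks for more than grayscale visibility. Section 6.3 states: "A region of interest encompassing the entire tumor volume and margin will then be selected in 4D mode", and line density may be adjusted to keep the acquisition rate above 0.5 volumes per second. If contrast is insufficient in either mode, sections 5.1 and 6.3 allow a repeat injection within a cumulative limit.

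For reading, sections 6.5 and 7.2 say that each reader "will be asked to evaluate all 201 remaining cases" and give two outcomes: "Intratumoral blood flow will be assessed as present or not present". Incomplete treatment on CEUS is "evidenced by the tumor showing either residual blood flow after treatment or nodular peripheral blood flow". For analysis, "Four 2 x 2 tables will be constructed", one for each combination of 2D or 4D with 1-2 weeks or 1 month. Discordant readings in the majority analysis go to consensus of two readers. Section 7.2.1 bases power on all 201 patients, that is, 210 less the 9 training cases.

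**The concern.** Visibility of a lesion on grayscale before TACE does not show that it can be assessed in 4D with contrast, or that it will still be assessable at 1-2 weeks and at 1 month. Some follow-up exams may therefore remain non-diagnostic, and the plan does not say how they are read, counted or reported.

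On a two-value form, a lesion with no flow and a lesion that could not be assessed can receive the same mark. If disease remains, a no-flow mark on an unreadable exam is a false negative. If it does not, the mark is a true negative that carries no information. Once the reads are done, the two situations cannot be reliably separated.

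This matters for the test of sensitivity and specificity against 90%. It also matters for the 2D versus 4D comparison: if the modes fail at different rates, the result mixes readability with accuracy on readable images, or rests on different patients.

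**Working it through.** **Inputs from section 7.2.1.** Null sensitivity and specificity 90%; alternative 98%; alpha 0.05; prevalence 66.7%; 201 patients analysed.

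**Input not in the documents.** The fraction f of follow-up exams that remain non-diagnostic. I assume 2%, 5% and 10%.

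**Reproducing the plan's power.** The test is exact binomial. The critical count is the smallest r with P(X ≥ r | 0.90) ≤ 0.05, one-sided. Sidedness is not stated, but the table reproduces only this way.
- Sensitivity, n = 133: r = 126, actual alpha 0.0385, power 0.9945.
- Specificity, n = 67: r = 65, actual alpha 0.0307, power 0.8494.

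Both match the plan's row for N = 200. Below I use 201 × 0.667 = 134 diseased (r = 127, power 0.994) and 201 − 134 = 67 non-diseased (r = 65). The sensitivity test therefore tolerates 134 − 127 = 7 misses, and the specificity test 67 − 65 = 2.

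**Case A: unreadable exams marked as no flow.** Se = 0.98(1 − f); Sp = 0.98(1 − f) + f; expected misses = 134(1 − Se).

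| f | Se | Expected misses (7 allowed) | Power, Se | Sp | Power, Sp |
|---|---|---|---|---|---|
| 0 | 98.0% | 2.7 | 99% | 98.0% | 85% |
| 2% | 96.0% | 5.3 | 84% | 98.0% | 86% |
| 5% | 93.1% | 9.2 | 29% | 98.1% | 87% |
| 10% | 88.2% | 15.8 | 1% | 98.2% | 88% |

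Expected sensitivity falls below the null when 0.98(1 − f) < 0.90, that is, f > 1 − 0.90/0.98 = 8.2%.

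**Case B: unreadable exams dropped.** If unreadability is unrelated to outcome and to reading difficulty, both estimates stay at 98% and only numbers are lost.
- f = 5%: 67 × 0.95 ≈ 64 non-diseased; two errors are still allowed; specificity power 86%.
- f = 10%: 67 × 0.90 ≈ 60 non-diseased; only one error is allowed; specificity power 66%. The plan's own table gives 0.6619 for 60.
- Sensitivity power is 99% at both values (n = 127 and 121).

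The exact test is saw-toothed, so the loss is not smooth in f. If unreadability is related to outcome or difficulty, the estimates are biased as well, by an amount the documents do not allow one to compute.

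**Case C: kept and counted as incorrect.** Se = Sp = 0.98(1 − f).
- f = 2%: 96.0% for both; power 84% for sensitivity, 50% for specificity.
- f = 5%: 93.1% for both; power 29% and 15%.
- f = 10%: 88.2% for both; power about 1% for each.

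Sensitivity is identical in A and C. Only specificity differs.

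**Effect on 2D versus 4D.** For one two-value read the ROC area is (Se + Sp)/2. Suppose both modes are 98% accurate on readable exams, 2D never fails, and 4D fails in 5%, marked as no flow. The areas are (0.98 + 0.98)/2 = 0.980 and (0.931 + 0.981)/2 = 0.956. The gap of 0.024 comes wholly from readability, and the two-value record could not show that.

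**The case against.** The plan does work to keep failures rare. Difficult lesions are pre-screened on grayscale. The first three cases at each site are guided by a study PI. Injection may be repeated, line density may be adjusted, and readers locate the mass on baseline CE-MRI/CT and CEUS first. All of this stands and may make f small. None of it says what happens to an exam that stays inadequate: consensus settles disagreement between readers, not unreadable images, and the rule that a missed 1-2 week exam does not bar the final one says nothing about analysing the gap.

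The size rests on an assumed f, which is also fair. At 2% the sensitivity test keeps 84% power. A reader might take the 10-30% in section 6.2 as a guide, but that is a baseline rate among patients who are then not followed, so it cannot serve as a follow-up rate.

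Under no-flow scoring the error mostly works against the trial's claim: with 98% accuracy on readable exams, specificity rises by only 0.1 to 0.2 points at f of 5% to 10%. That is correct and limits the concern about false success. It does not help a trial whose sensitivity result could turn on an unwritten convention.

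Finally, counting non-diagnostic reads as incorrect is only one defensible primary rule. It does not restore sensitivity, and it is severe on specificity. I agree that the choice belongs to the sponsor.

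**Conclusion.** The gap is real: a stated two-value read and 2 x 2 tables leave no place for a non-diagnostic follow-up exam, and the only visibility rule is at baseline. It should be corrected before reading begins, because the information cannot be reliably recovered afterwards.

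The size is conditional. With 98% accuracy on readable exams, marking 2%, 5% or 10% of exams as no flow takes sensitivity to 96.0%, 93.1% or 88.2%, and its power from 99% to 84%, 29% or 1%. The true rate is unknown.

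Three stronger readings are not supported:
- That the plan scores such exams as completely treated, or silently drops them. It says neither. No flow is the natural default because a positive requires flow to be shown, but a forced positive or a blank is also possible.
- That dropping inflates both measures. It does so only if unreadability goes with harder or differently distributed outcomes. Section 6.2 links poor baseline visibility to small dome lesions in cirrhosis, which makes this plausible but does not establish it for follow-up.
- That the loss of sensitivity is a bias the third category removes. Under counted-as-incorrect scoring sensitivity is the same. What the category adds is a visible failure rate and a rule chosen in advance.

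**What to change.** In sections 6.5 and 7.2:
1. Change the CEUS read to three values (present, not present, non-diagnostic), recorded per reader, mode and time point.
2. Report the non-diagnostic rate for each of the four CEUS groups.
3. Give sensitivity and specificity in two ways: for assessable exams only, and with non-diagnostic reads counted as incorrect against either reference state. The sponsor names the primary version before reads start.
4. Compare 2D with 4D on the same patients.

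The cost in work is one form field, some extra tables and a few sentences; no additional imaging or reads are needed. The cost in results may be material. If the counted-as-incorrect version is primary, specificity power is about 50% at 2% non-diagnostic and 15% at 5%. If the assessable-only version is primary, precision falls (specificity power 66% at 10%) and the estimate applies only to readable exams. The sample size has no allowance for either, so the sponsor should make the choice with these figures in view.
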